Direct motoric and cognitive interaction with a physical and occupational therapist remains the mainstay of rehabilitation therapy for residual motor impairment in the United States. Among ischemic stroke patients with a moderate to severe disability at the end of the acute care hospital

phase, multiple studies have demonstrated the typical subsequent course is some improvement in deficits over the next 3 months followed by stabilization at a permanent level of functioning. Multiple studies have shown that, with standard rehabilitative care, moderately-severely disabled patients improve by a mean of around 1.1 points on the mRS scale by day 90 (46-48). Taking into account this improvement, the mRS level at the conclusion of acute care, upon stabilization from acute injury is strongly and consistently correlated with mRS at day 90 (49). This improvement is consistent across broad patient groups, regardless of age, sex, and ischemic stroke mechanism. However, this improvement is typically incomplete, and most patients are then left with residual, permanent disability.

Some technologies have been tested, generally in small trials, for potential to further improve recovery above this standard of care, including neuromuscular electrical stimulation (NMES), functional electrical stimulation (FES), and robot-assisted therapy (50, 51). Although of some promise, none of these devices has been yet demonstrated to be unequivocally beneficial and none are deemed to be elements in the current standard of care in the United States (43).

In sum, although there are demonstrated benefits of select acute ischemic stroke therapies and PT/OT rehabilitation programs for stroke, a substantial majority of stroke patients, roughly 90% (2), are left with persisting, lifelong impairments despite receiving the current standard of care. Thus, while the standard of care may be effective and allow for a meaningful reduction in disability, for those patients with a moderate to severe disability, these changes are often insufficient. In these patients, a chronic disability persists, not allowing them to return to work or participate in their usual pre-stroke activities.

Potential role of the investigational device

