5 STUDY POPULATION

5.1 INCLUSION CRITERIA

In order to be eligible to participate in this study, an individual must meet all of the following criteria:

1. mRS score of 3 or 4.
2. FMA-UE score between 10-45 (inclusive) of impaired limb.
3. Age 22 to 85 years of age (inclusive).
4. Diagnosed with an ischemic stroke, confirmed by CT²¹ or MRI²² imaging.
5. Four to 21 days from stroke onset (or last known well).
6. Pre-stroke mRS of 0 or 1.
7. Able to sit with the investigational device for 40 consecutive minutes, in the opinion of the investigator or designee.
8. Can follow a 3-step command, such as “take the paper, fold it in half, and return it to me”.
9. Willingness to participate in occupational/physical therapy activities during study intervention sessions.
10. Availability of a relative or other caregiver able to assist during PT/OT treatment, and to operate an application installed on a mobile device, including a video call.
11. If female, not pregnant (as confirmed by a urine or a blood test, or as determined by an official medical document) or breastfeeding and with no ability to become pregnant or on an acceptable method of contraception during the study
12. Informed consent signed by subject (if competent) or legally authorized representative.

²⁰ 42 CFR Part 11 § 11.10(a)(3) “completion date” or “primary completion date” synonymous to the “completion date” defined in section 402(j)(1)(A)(v) of the Public Health Service Act [42 U.S.C § 282(j)(1)(A)(v)]

²¹ Computed tomography

²² Magnetic resonance imaging

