6.3 MEASURES TO MINIMIZE BIAS: RANDOMIZATION AND BLINDING

6.3.1 ALLOCATION TO STUDY INTERVENTION

After informed consent has been elicited from the subject or his/her legally authorized represented, and the subject is determined to fully meet the study eligibility criteria, he/she will be equally allocated (with a 1:1 ratio) to one of the following 2 treatment groups based on a permuted block randomization scheme with blocks stratified by site, age (22-69, 70-85) and mRS score at baseline (3 vs 4):

- BQ 2.0 active stimulation group
- BQ 2.0 sham stimulation group

Allocation (randomization) of participants to study groups will proceed through the use of the EDC system (Syncrony) for randomization and the BQ 2.0 Administrator Panel for treatment allocation. The site personnel (Study Coordinator or specified designee) will be required to enter or select information including but not limited to the user's ID and password, the protocol number, and the participant number. The site personnel will then be provided with a group assignment and randomization number. The Syncrony system will provide to the unblinded site personnel the study intervention allocation assigned. The randomization schedule and treatment arm assignments will be kept by Syntactx-NAMSA data manager with appropriate security measures and access control.

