9.4.2 ANALYSIS OF THE PRIMARY ENDPOINT

The primary endpoint, mRS change from baseline (day 4-21 post-stroke) to 90 days post-stroke, will be compared between the treatment groups using repeated measures analysis of covariance (ANCOVA, SAS® MIXED procedure).

The model will include the following fixed effects: treatment group, visit [categorical – midterm follow-up visit (± 4 days from 20th treatment) and Day 90 follow-up visit (day 90 ± 15 days post-stroke)], treatment group by visit interaction with baseline mRS and age entered as covariates. Age will be entered as a continuous variable so that the potential for co-linearity problems will be minimized. Center will be entered as a random effect. The treatment group by site interaction will be evaluated as well, but not as part of the principal statistical evaluation.

The compound symmetry covariance structure will be used. If the model does not converge, then either the unstructured or autoregressive (AR1) (whichever model has the lower Akaike information criterion statistic) covariance matrix structure will be used instead. At this time point (up to 3 months post stroke), we do not expect a high proportion of dropouts, as a placebo effect of the sham treatment is expected and was taken into consideration in the design of the study. Thus, any missing data at this time point can be considered missing at random. Therefore, since likelihood based repeated measures is also an imputation method, for this evaluation no other method of imputation of missing data is considered beyond the model estimates. Nevertheless, should the missing at random assumption prove to be incorrect, a sensitivity analysis using methods for data imputation may be performed, such as last observed value (LOV) of that endpoint (115). The LOV is defined as the last available post baseline visit data up to and including the last treatment visit or termination visit. Additionally, we may consider multiple

	The efficacy of a frequency-tuned electromagnetic field treatment in facilitating the recovery of subacute ischemic stroke patients – a pivotal study		
	No. BQ5	Ver. 4	Page 81 of 150

imputation using a model incorporating key baseline prognostic features as well as the last post-randomization if deemed necessary.

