9.4.7 SUB-GROUP ANALYSES

Subgroup analysis of the primary efficacy endpoint such as demographic or other baseline patient characteristics will be performed. **Potential Sub-groups**

1. Sex
2. Age groups (< 70 vs. ≥ 70 years)
3. Race
4. Ethnicity
5. mRS 3 vs. 4
6. FMA-UE score
7. 10MWT score
8. Received tPA/thrombectomy for the index stroke
9. SAFE score at baseline (<5, 5-7, 8 or more)
10. First stroke or not
11. Right/left sided stroke
12. Stroke mechanism
13. Time from event to first treatment (< 14 days vs. ≥ 15 days)

14. Compliant vs. not-compliant⁵⁰
15. Treatment group assignment guess by the subject (blinding assessment)

Pooling

Subgroup analysis of the primary efficacy endpoint by site will be used to evaluate the poolability of the results. The significance of site-to-site variability in treatment effect will be evaluated by including site to the visit by group interaction term and will be added to the primary model. If the interaction time by site by group is found significant at a 15% level of significance, the reason for this will be further explored and rationalized. This evaluation may include demographic and baseline features, clinical and treatment history, and site comparability in the features found to be associated with the primary efficacy variable.

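### The primary model omits days from stroke onset to baseline, a recorded and probably prognostic variable; the cost is some precision and unadjusted chance imbalance, not validity.

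*Protocol*

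**What the plan says.** Section 9.4.2 defines the primary endpoint as "mRS change from baseline (day 4-21 post-stroke) to 90 days post-stroke". The model has treatment group, visit (midterm and day 90), "treatment group by visit interaction with baseline mRS and age entered as covariates". It adds that "Center will be entered as a random effect". Time since stroke is not among the terms.

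Inclusion criterion 5 in section 5.1 reads "Four to 21 days from stroke onset (or last known well)". Section 6.3.1 randomizes in "blocks stratified by site, age (22-69, 70-85) and mRS score at baseline (3 vs 4)", so allocation is not balanced on time since stroke either.

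Stroke timing is used once, in the list of potential subgroups in section 9.4.7: "Time from event to first treatment (< 14 days vs. ≥ 15 days)". As written, day 14 falls in neither group.

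On the natural course, section 2.2 says that patients show "some improvement in deficits over the next 3 months followed by stabilization at a permanent level of functioning" and that with standard care "moderately-severely disabled patients improve by a mean of around 1.1 points on the mRS scale by day 90". Section 4.2 justifies the 4-21 day window as the period when neural reorganization is greatest.

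**The concern.** If patients on standard care are recovering during days 4-21, a patient scored mRS 4 on day 4 and one still at mRS 4 on day 21 do not have the same outlook. The second has already used up part of the recovery period without leaving that level. The model treats them alike, because eligible baseline scores are only 3 or 4 and baseline mRS is the only severity term. Centre as a random effect can absorb differences in average timing between sites, but not differences between patients within a site.

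Two things are at stake. Variation that could be explained stays in the residual and costs some power. And if the arms differ by chance in mean baseline day, the estimated effect moves with that difference and the model does not adjust for it. The interim matters as well: 78 evaluable subjects decide between futility, sample-size increase and continuation, and the imbalance to be expected there is larger than at 128.

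**Working it through.** **Inputs from the protocol.** Difference 0.5, SD 1, 80% power, two-sided 5%, 64 per arm (section 9.2); mean improvement of about 1.1 points by day 90 on standard care (section 2.2); window of days 4-21 (section 5.1); interim at 78 evaluable of 128, with conditional-power limits of 32.7375% and 80% (section 9.4.6).

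**Inputs assumed, not in the protocol.**
- Slope of the outcome on baseline day: 0.0128 per day (1.1 points spread evenly over 90 − 4 = 86 days) up to 0.0655 per day. The upper value is roughly all 1.1 points recovered between days 4 and 21: 1.1/17 = 0.065, and 17 × 0.0655 = 1.11. Intermediate values are 0.03 and 0.05.
- Spread of baseline days: uniform on the 18 days 4-21, SD = √((18² − 1)/12) = 5.19 days; or concentrated, SD = 3 days.

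**1. The plan's own figure.** A two-sample t-test with 64 per arm, df 126 and noncentrality 0.5/√(2/64) = 2.83 gives power 80.1%. The stated total of 128 is reproduced.

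**2. Gain from adjustment.** Share of variance explained R² = (slope × SD of day)², since the outcome SD is 1. Residual SD = √(1 − R²). Power is from the noncentral t at 64 per arm.

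**3. Chance imbalance.** The SE of the arm difference in mean day is SD of day × √(2/64), which is 0.92 days under uniform days and 0.53 days at SD 3. Multiplied by the slope it gives the 1-SE shift in the treatment estimate.

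| Slope per day | R², uniform | Power, uniform | Total N for 80%, uniform | 1-SE shift, uniform | Power, SD 3 | 1-SE shift, SD 3 |
|---|---|---|---|---|---|---|
| 0.0128 | 0.4% | 80.3% | 128 | 0.012 | 80.2% | 0.007 |
| 0.03 | 2.4% | 81.1% | 126 | 0.028 | 80.5% | 0.016 |
| 0.05 | 6.7% | 82.8% | 120 | 0.046 | 81.0% | 0.027 |
| 0.0655 | 11.6% | 84.7% | 114 | 0.060 | 81.7% | 0.035 |

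At the edge of the 95% range (1.96 SE) the shift under uniform days is 0.02 to 0.12 points. For comparison, the SE of the treatment difference itself is √(2/64) = 0.18.

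**4. Validity.** A simulation with 10,000 runs per setting, 64 per arm and uniform days, analysed without the covariate, gave type I error of 4.8% to 5.4%. Under a true difference of 0.5 the mean estimates were 0.499 to 0.501. Omission gives neither bias nor inflation.

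**5. Interim, 39 per arm.** Under uniform days the SE of the difference in mean day is 5.19 × √(2/39) = 1.17 days. The 1-SE shift is then 0.015, 0.035, 0.059 and 0.077 points for the four slopes. Take conditional power under the observed trend as Φ((z/√t − 1.96)/√(1 − t)), with t = 78/128 = 0.609 and z = difference/√(2/39). The promising zone then runs from an observed difference of 0.30 to one of 0.44, a width of 0.14. A 1-SE imbalance is therefore worth about a tenth (0.015/0.14) to just over half (0.077/0.14) of that width. The ordinary sampling error of the difference at this stage, √(2/39) = 0.23, is already wider than the zone, so baseline day is one contributor among others.

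**The case against.** A reader might infer that the endpoint itself is unstable, because change is measured over anything from 54 days (day 21 to day 75) to 101 days (day 4 to day 105). The protocol does not support that reading. Baseline mRS is a covariate, so analysing change or day-90 mRS gives the same treatment estimate; only the baseline coefficient moves, by 1. The comparison is in effect of mRS at a visit anchored to stroke onset, and interval length drops out. Moreover, 30 of the 47 days of spread (101 − 54) come from the ±15-day visit window, which a term for baseline day does not touch. What remains is an ordinary omitted prognostic covariate.

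A reader might also infer bias or a loose error rate. Randomization rules both out, and chance imbalance is already reflected in the standard error.

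The size is open to challenge too. The slopes come from an unconditional recovery curve, not from recovery at a given mRS of 3 or 4, and the calculation is for a t-test at one time point, not for the planned model. Uniform days may be too wide, since sections 1.1 and 8.1.1.2 press for early enrolment. All of this stands, and it is why the low end of the range must be shown.

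Finally, section 9.4.1 lets the SAP override the protocol, timing is a potential subgroup, and imputation is to use key baseline prognostic features. These make the repair easy but do not make it: section 9.4.2 names its covariates and this is not one of them, and a subgroup table does not adjust the primary estimate.

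**Conclusion.** The point stands as a modest matter of precision. Days from stroke onset to baseline is known before randomization, is likely on the protocol's own account to predict outcome, and is not replaced by a baseline score with two values. Under the assumptions shown, adjusting for it is worth 0.2 to 4.6 percentage points of power with uniform baseline days (0 to 14 evaluable patients), and 0.1 to 1.6 points if the SD is 3 days. A 1-SE imbalance at the final analysis moves the estimate by 0.01 to 0.06 points under uniform days, against the 0.5-point target. The assumed slope and spread drive every one of these figures. At the near-linear slope the gain is negligible; the steepest slope is an upper bound. Nothing here puts the validity of the primary test in doubt.

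**What to change.** In section 9.4.2, add days from stroke onset (or last known well) to baseline mRS as a continuous fixed covariate, together with its interaction with visit. The interaction is needed because a single main-effect term would force the same slope at the midterm visit and at day 90, although less of the remaining recovery will have occurred by midterm. State in section 9.4.6 that the interim treatment difference comes from the same model.

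The cost is 2 df and no new data: onset is needed for inclusion criterion 5, and section 8.1.1.2 ties the baseline mRS to within 24 hours of randomization. The change should be fixed before any unblinded look, because adding the term after an imbalance has been seen would look data-driven.

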9.2 SAMPLE SIZE DETERMINATION

A sample size is calculated to test the null hypothesis with 80% power at a 5% two-sided level of significance using a two sample-t-test for simplicity, even though the main statistical analysis may employ a statistically more powerful model-based approach. The estimates used for the mean and standard deviation of the changes from baseline to day 90 are taken from the literature as well as company pilot study data. In the pilot study, the mean change in mRS score from baseline to week 9 in the treatment group was -2.5 (SD=0.66) versus -1.3 (SD=0.46) in the sham group. In the literature a difference of 0.06 points on the mRS between treatment groups is considered clinically meaningful (114). As powering the trial to detect this difference would yield infeasibly large sample sizes, sample size projections were based on detecting a difference as low as 40% of the difference seen in the pilot trial = 0.5-point. To detect a 0.5-point difference between the groups with 80% power at a 5% level of significance using a standard deviation of 1 point and 1:1 allocation ratio, the calculated sample size (PROC POWER in SAS V9.4) is 128 participants in total, 64 participants in each arm. Allowing for a 15% dropout, 150 participants should be randomized.

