9.4 STATISTICAL ANALYSES

9.4.1 GENERAL APPROACH

Statistical analyses will be performed using SAS® v9.4 or higher (SAS Institute, Cary, NC, USA). Statistical analyses and reporting will be performed in compliance with FDA Guidance E6 and E9 and ISO 14155;2020.

Study data will be summarized with descriptive statistics and presented in tables and figures. Continuous variables will be summarized by a mean, standard deviation, minimum, median, and maximum and categorical variables by a count and percentage. For comparison of continuous variables, the two-sample t-test or the Wilcoxon rank sum test will be used as appropriate. For comparison of proportions (categorical variables), the chi-squared test or Fisher's exact test will be used as appropriate. A Cochran-Armitage trend test may be used when the response is ranked. For comparison of time to event data, the log-rank test will be used. If multiple measurements are taken in a single subject, statistics described below will be appropriately modified to accommodate the within subject correlation.

Detailed methodologies of the statistical analyses of the data collected in this study will be outlined in a trial-specific Statistical Analysis Plan (SAP). Any changes to planned analyses will be described and justified in the SAP. Analyses outlined in the SAP take precedent over those defined in the protocol to the extent there are any conflicts between the two documents.

Significance Levels and Type I Error

The overall significance level for this study is 5% using two-tailed tests, except for the group by site interaction that will be tested at a significance level of 15%.

The hierarchy (stepwise gatekeeper) approach will be adopted for the primary and secondary endpoints to control type I error due to multiple endpoint testing.

The primary endpoint will be analyzed first and only if the null hypothesis is rejected at a 5% level of significance or lower then we shall continue to test the secondary endpoints in a hierarchical manner. Nominal p-values will be reported, even if eventually due to the hierarchy the result is not considered statistically significant.

	The efficacy of a frequency-tuned electromagnetic field treatment in facilitating the recovery of subacute ischemic stroke patients – a pivotal study		
	No. BQ5	Ver. 4	Page 80 of 150

The hierarchical order of analysis of the secondary endpoint family will be:

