The principal statistical analysis will be a comparison between the treatment groups, derived from the visit by treatment group interaction term from the model. The adjusted mean change from baseline in mRS scores at the 90 days post-stroke visit will be estimated from the model (LS Means) interaction term for each group as well as for the difference between the adjusted means and presented together with 95% confidence intervals and level of significance.

The null hypothesis will be rejected in favor of the alternative hypothesis and the study deemed successful if the P value is <0.05 and the mean change mRS in the BQ 2.0 group is higher than that of the sham group at the 90 days post stroke visit.

A shift analysis of the primary endpoint will be performed as a sensitivity analysis as well.

Handling of Missing Primary Endpoint Data

By the 90 days post-stroke visit, we do not expect a high proportion of dropouts, as a placebo effect of the sham treatment is expected and was taken into consideration in the design of the study by using conservative estimates of the treatment effect.

All subjects with at least 1 post-baseline measurement will be included in the statistical analyses. The primary endpoint will be analyzed using a likelihood based repeated measures model, which can handle data missing at random.

For the mITT set, missing primary outcome data at day 90 will be imputed with multiple imputation using a model incorporating key baseline prognostic features as well as the last post-randomization observed value (LOV) of that endpoint (115). The LOV is defined as the last available post baseline visit data up to and including the last treatment visit or termination visit. The LOCF imputation method will also be used to carry forward the most recent data prior to withdrawal/dropout as a sensitivity analysis.

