The study will either continue to the originally planned sample size if the result is “favorable”, stop for futility if the result is “unfavorable” or an increase will be made to the sample size if the result is “promising”. These decisions will be made based on the conditional power (CP), defined as the conditional probability that the result will exceed a critical value at the interim given the observed effect size $\hat{\delta}_1$ = difference between mean change from baseline mRS score for the BQ 2.0 versus sham groups at the interim look.

Notation:

- n1= sample size at interim analysis.
- n2= original sample size calculated based on assumed effect size.

nmax = the highest sample size the company is willing to use, nmax = 292 subjects (344 randomized including an allowance for a 15% dropout), and is based on a potential smaller effect size of ~0.33.

CPmin = is the calculated minimum CP based on the ratios nmax/n2, n1/n2 and the target study power (80%).

The following are the decision rules for the interim analysis which will be performed upon accrual of ~61% (n1/n2) of the originally planned sample size, ie, 78 evaluable subjects. These depend on the zone into which CP falls at the interim, the calculated CPmin, the maximum sample size designated for the study and the % of the originally planned sample size at which the interim analysis will be performed. Following this principle does not inflate the Type I error.

	The efficacy of a frequency-tuned electromagnetic field treatment in facilitating the recovery of subacute ischemic stroke patients – a pivotal study		
	No. BQ5	Ver. 4	Page 84 of 150

- If the result is “Unfavorable”, ie, $CP < CP_{min} = 32.7375\%$, ie, interim result is so disappointing that it is not worth increasing the sample size to retrieve conditional power, stop the trial for futility.
- If the result is “Promising”, ie, $32.7375\% \leq CP < 80\%$ for the primary endpoint, the sample size is increased to recover the targeted power of 80%. The sample size used will be either the new calculated sample size based on the conditional power (117) or the predetermined maximum sample size of 292 (344 randomized including an allowance for a 15% dropout) subjects, whichever lower.

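### The primary two-visit model fixes compound symmetry and drops it only on non-convergence, so the day-90 standard error, CI and P value rest on an unsupported equal-variance assumption

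*Protocol*

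**What the plan says.** Section 9.4.2 of the protocol analyses mRS change with a repeated-measures mixed model. The fixed effects are treatment, visit (midterm and day 90) and their interaction, with baseline mRS and age as covariates and center as a random effect. On the covariance of the two visits it says "The compound symmetry covariance structure will be used". The only way out is "If the model does not converge, then either the unstructured or autoregressive (AR1"; AIC chooses between those two, but only after non-convergence.

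The day-90 adjusted means, their difference, the 95% CI and the P value all come from this model, and the rule for success is "the study deemed successful if the P value is <0.05 and the mean change mRS in the BQ 2.0 group is higher" than in the sham group at day 90. The same section adds that for the mITT set "missing primary outcome data at day 90 will be imputed with multiple imputation".

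Section 9.2 gives the only SDs in the document: 0.66 and 0.46 for the pilot change to week 9, and a planning calculation "using a standard deviation of 1 point and 1:1 allocation ratio". Section 9.4.1 states "Analyses outlined in the SAP take precedent over those defined in the protocol" where the two conflict.

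**The concern.** Compound symmetry has one variance and one correlation. With midterm and day 90 in the same model, the day-90 contrast gets a standard error based on the average of the two visits' residual variances, although only the day-90 variance is relevant to it. If mRS change is less variable at midterm than at day 90, the CI is too narrow and the P value too small. If it is more variable at midterm, the CI is too wide and power is lost.

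The safeguard does not address this. A model with the wrong variance pattern converges normally. One of the two fallbacks is no alternative: with two visits AR(1) also has one variance and one correlation, so it is the same matrix as compound symmetry. The unstructured matrix, the only one that lets the variances differ, is reached only after the simpler model has failed.

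The decisive test of the trial therefore depends on a ratio of SDs that the protocol neither reports nor checks.

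**Working it through.** **Inputs.** From section 9.2: difference 0.5, SD 1, two-sided 5%, 80% power, 64 per arm. From section 9.4.6: interim look at 78 of 128 evaluable, stop below a conditional power of 32.7375%, increase to at most 292 if below 80%. Assumed, because the protocol gives no midterm SD: r = SD(midterm)/SD(day 90), shown from 0.7 to 1.25.

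**The plan's own figure.** The noncentral t gives 79.5% power with 63 per arm and 80.1% with 64, so 128 evaluable is reproduced. Dividing by 0.85 gives 150.6, against the stated 150.

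**Step 1: fixed sample, complete data.** The day-90 estimate is the same under both structures. The ratio of the compound-symmetry standard error to the true one is

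f = sqrt((r² + 1)/2).

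The two-sided rejection rate under the null is 2 × [1 − Φ(1.96 f)], and CI coverage is its complement. Example, r = 0.8: f = sqrt((0.64 + 1)/2) = 0.906, so the rate is 2 × [1 − Φ(1.775)] = 7.6%.

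Power for 0.5 points is 1 − Φ(1.96 f − 0.5/sqrt(2/64)), with 0.5/sqrt(2/64) = 2.828. At r = 1 this is 1 − Φ(1.960 − 2.828) = 80.7%. At r = 1.25, f = 1.132 and it is 1 − Φ(2.219 − 2.828) = 72.9%.

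**Step 2: the planned adaptive design.** This was simulated under the null with 8 million runs per r. Success counts only in favour of BQ 2.0, reading the direction in the success rule as greater improvement, so the nominal rate is 2.5%. Section 9.4.6 describes conditional power as "defined as the conditional probability that the result will exceed a critical value at the interim given the observed effect size", which was taken as current-trend conditional power. The protocol does not say which model supplies the interim standard error, so two cases were run: (A) the same f at both looks; (B) a correct standard error at the interim and compound symmetry only at the final analysis. Section 9.4.6 states the futility stop as a rule, while section 10.1.6 says only that the DSMB may consider recommending a stop, so both enforced and not enforced are shown.

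| r | f | Fixed sample: two-sided rejection / coverage | A: false success, enforced / not | B: false success, enforced / not |
|---|---|---|---|---|
| 0.7 | 0.863 | 9.1% / 90.9% | 3.39% / 4.44% | 2.82% / 4.27% |
| 0.8 | 0.906 | 7.6% / 92.4% | 2.83% / 3.70% | 2.49% / 3.58% |
| 0.9 | 0.951 | 6.2% / 93.8% | 2.31% / 3.02% | 2.17% / 2.97% |
| 1.0 | 1.000 | 5.0% / 95.0% | 1.85% / 2.42% | 1.84% / 2.41% |
| 1.25 | 1.132 | 2.7% / 97.3% | 0.97% / 1.27% | 1.13% / 1.33% |

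Break-even with 2.5%: enforced, about r = 0.86 in case A (2.52% at 0.86, 2.50% at 0.865) and about 0.80 in case B (2.49% at 0.8). Not enforced, r = 0.985 in case A. In case B, linear interpolation between 0.9 and 1.0 gives 1.0 − 0.1 × (2.50 − 2.41)/(2.97 − 2.41) = 0.984.

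**Step 3: does the unstructured matrix remove the dependence?** A complete-data simulation used 64 per arm, an assumed visit correlation of 0.6 and 100,000 null replicates. At r = 0.7 / 0.8 / 0.9 / 1.0 / 1.25, two-sided rejection was 8.9 / 7.6 / 6.1 / 4.8 / 2.6% with compound symmetry and 5.0 / 5.1 / 5.0 / 4.9 / 5.0% unstructured. Power at r = 1.25 was 72.3% against 80.2%.

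A smaller REML check with 75 per arm and day-90 values missing at random (800 runs each) gave, compound symmetry against unstructured, 7.0% against 4.0% at r = 0.8, 4.6% against 5.3% at r = 1.0 and 2.5% against 5.0% at r = 1.25. With 800 runs a 5% rate has a simulation standard error of sqrt(0.05 × 0.95/800) = 0.8 points.

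**Not modelled:** the baseline and age covariates, the random center effect, and the multiple imputation specified for the mITT set.

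**The case against.** The case for leaving the sentence alone is serious. Compound symmetry is a recognised structure, named in advance with an ordered fallback, and nothing in section 9.4.2 contradicts anything else. All of the harm depends on r. The relevant r is a ratio of residual SDs after baseline mRS, age and center, so even a raw midterm SD would not settle it. If the variances are equal nothing is lost, and if midterm is the more variable the test is conservative. The fixed-sample rates ignore the interim look and count rejections in both directions, so they are not the trial's false-success rate. Section 9.4.6 instructs that if "it is not worth increasing the sample size to retrieve conditional power, stop the trial for futility", without calling this optional; with that stop enforced the rate is 1.9% at r = 1.0 and 2.3% at r = 0.9, both under 2.5%. The planned shift analysis is a further check on the primary result. Finally, the SAP overrides the protocol and may name another structure.

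Most of this stands, and it limits the weight of the point: no error is demonstrated and the direction is open. It does not remove the point. The protocol positively fixes the structure rather than leaving it to the SAP. The futility stop offsets the excess only above r of about 0.80 to 0.86 and does nothing for the power lost when r exceeds 1. A shift analysis does not correct the primary CI or P value, and imputing missing values does not undo the pooling of variances in the analysis model.

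**Conclusion.** The concern holds as a free improvement, with moderate confidence. The day-90 standard error, CI and success P value depend on equal residual variances at midterm and day 90, which the protocol neither supports nor checks, and the convergence trigger would not detect a failure of that assumption.

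The size depends on the undocumented r. There is no error at r = 1. Below 1, fixed-sample coverage falls to 93.8%, 92.4% and 90.9% at r = 0.9, 0.8 and 0.7. In the planned design with the futility stop enforced, false success for BQ 2.0 reaches 2.5 to 2.8% at r = 0.8 and 2.8 to 3.4% at r = 0.7, depending on the interim model. Without enforcement it is 3.6 to 3.7% and 4.3 to 4.4%. Above 1 the cost is power, 7.8 points at r = 1.25 (80.7 − 72.9). The design figures assume current-trend conditional power and complete data.

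**What to change.** In section 9.4.2, replace the compound-symmetry sentence and its fallback with: *An unstructured covariance matrix over the two visits will be used; compound symmetry will be used only if that model does not converge.* Delete AR(1), which adds nothing with two visits. Further fallback detail can stay in the SAP, and if the SAP already specifies an unstructured matrix, the protocol sentence should be aligned with it.

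The cost is one sentence and one extra variance parameter (three instead of two) with about 128 evaluable patients. If the variances really are equal, power for 0.5 points goes from 80.4% (about 250 df) to 80.1% (about 124 df), a loss of about 0.3 points. No added patients, visits or data are needed, and the sample size of 128 is unchanged.
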